5.2.1.2.2. Derived urine and fecal pharmacokinetic parameters

- Derivation of urine and faecal radioactivity parameters will be the responsibility, or under the direct auspices, of the DMPK department within GSK.
- When summarizing urine and faecal parameters, 'NS' (i.e., no sample provided as subject not voided at particular collection period) or 'NQ' values for these parameters will be imputed with zero.

Table 5 Derived urine and faeces pharmacokinetic parameters

Parameter	Parameter Description
Ae[urine]	Total radioactivity recovered in the urine (Ae[urine]) calculated for each collection interval per subject and treatment period as: Ae[urine]= (concentration in urine sample x collected sample weight) for each urine collection interval, eg 0-24, 24-48, etc.
Cumulative Ae[urine]	Cumulative total radioactivity recovered in the urine (Cumulative Ae[urine]) calculated for each cumulative collection interval per subject and treatment period as: Cumulative Ae[urine] = summation of Ae[urine] For each urine collection with the cumulative urine collection interval
Fe%[urine]	% of total dose excreted as total radioactivity (Fe%[urine]) for each collection interval per subject and treatment period, estimated as: Fe%[urine]=(Ae[urine] for each collection period)/Dose*100. Where the dose is the radiolabelled [¹⁴ C]-GSK3640254, that is in period 1 radiometric iv dose, in period 2 radiometric oral dose
Cumulative Fe%[urine]	Cumulative % of total dose excreted as total radioactivity (Cumulative Fe%[urine]) for each cumulative collection interval per subject and treatment period, estimated as: Cumulative Fe%[urine]= summation of Fe[urine] Where the dose is the radiolabelled [¹⁴ C]-GSK3640254, that is in period 1 radiometric iv dose, in period 2 radiometric oral dose
Ae[faeces]	Total radioactivity recovered in the urine (Ae[faeces]) calculated for each collection interval per subject and treatment period as: Ae[urine]= (concentration in urine sample x collected sample weight) for each urine collection interval, eg 0-24, 24-48, etc.
Cumulative Ae[faeces]	Cumulative total radioactivity recovered in the urine (Cumulative Ae[faeces]) calculated for each cumulative collection interval per subject and treatment period as:

CONFIDENTIAL

Statistical Analysis Plan 213051

Parameter	Parameter Description
	
Cumulative Ae[faeces] = summation of Ae[faeces]
 
For each urine collection with the cumulative urine collection interval

Fe%[faeces]	
% of total dose excreted as total radioactivity (Fe%[faeces]) for each collection interval per subject and treatment period, estimated as:
 
$Fe\%[urine] = (Ae[faeces] \text{ for each collection period}) / Dose * 100.$
 
Where the dose is the radiolabelled [¹⁴C]-GSK3640254, that is in period 1 radiometric iv dose, in period 2 radiometric oral dose

Cumulative Fe%[faeces]	
Cumulative % of total dose excreted as total radioactivity (Cumulative Fe%[faeces]) for each cumulative collection interval per subject and treatment period, estimated as:
 
Cumulative Fe%[faeces]= summation of Fe[faeces]
 
Where the dose is the radiolabelled [¹⁴C]-GSK3640254, that is in period 1 radiometric iv dose, in period 2 radiometric oral dose

Ae[total]	
Total radioactivity recovered in total excretum (sum of urine and faecal excretion) Ae[total] will be estimates by collection interval for each subject and treatment period as:
 
$Ae[total] = Ae[urine] + Ae[faeces]$

Cumulative Ae[total]	
Total radioactivity recovered in total excretion (sum of urine and faecal excretion), cumulative Ae[total] will be estimates by cumulative collection interval per subject and treatment period as:
 
Cumulative Ae[total]= summation of Ae[total]
 
for each total excretion collection within the cumulative total excretion collection interval, eg 0-24, 0-48, etc

Fe%[total]	
% of total dose excreted as total radioactivity (Fe%[total]) for each collection period will be estimated for each subject and treatment period as:
 
$Fe\%[total] = Fe\%[urine] + Fe\%[faeces]$

CONFIDENTIAL

Statistical Analysis Plan 213051

Parameter	Parameter Description
Cumulative Fe%[total]	
Cumulative % of total dose excreted as total radioactivity (Cumulative Fe%[total]) for each cumulative collection period will be estimated for each subject and treatment period as:
 
Cumulative Fe%[total]= Cumulative Fe%[urine]+ Cumulative Fe%[faeces]
 
for each total excretion collection within the cumulative total excretion collection interval, eg 0-24, 0-48, etc

Notes: additional parameters may be included as required

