GlaxoSmithKline have provided experimental data on the biokinetics of [¹⁴C]GSK3640254 mesylate following its oral administration to pigmented and albino rats. The data have been used to determine the likely dose to male volunteers from a single administration of the radio-labelled compound. The assumption is made that the levels of uptake and retention by tissues will be the same in man as in the experimental animals. Committed equivalent doses to tissues and organs and committed effective dose (E(50)) have been calculated according to the 1990 Recommendations of the International Commission on Radiological Protection (ICRP)¹ as implemented in the Ionising Radiations Regulations 1999² in response to EU Council Directive 96/29/Euratom³. ICRP Publication 105⁴ recommends the use of dose constraints, where the exposure of volunteers in biomedical research provides no direct benefit to them, to limit any inequity between individual risk and societal benefit and because there is no specific further protection in the form of a dose limit. The E(50) can be compared with the dose categories proposed for research projects involving human volunteers by the World Health Organization (WHO)⁵ and ICRP⁶.

2. Data used in calculations

Results were provided for the urinary and faecal excretion of ¹⁴C following the oral administration of [¹⁴C]GSK3640254 mesylate to albino rats. Expressed as percentages of total excretion, the values used for the calculations were 0.04% urinary and 99.96% faecal excretion.

Data were provided for the tissue distribution of ¹⁴C after oral administration of [¹⁴C]GSK3640254 mesylate to pigmented rats. Concentrations of radio-labelled compound retained in the tissues were expressed as nanogram equivalents per gram (ng eq/g) of tissue. These concentrations were converted to values for the percentage of administered activity retained in individual tissues or organs using standard organ weights⁷. Doses were calculated using values for 21 tissues at 5 time-points between 1 and 240 hours after administration. Retention half-time data were provided for the eye on the basis of measurements in pigmented rats; a half-time of 23.2 hours was estimated.

3. Method of calculation

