5.2.1. Definition of endpoint(s)

- AUC(0-inf), AUC(0-t), C_{max}, t_{max} and t_{1/2} of parent and total drug-related material (radioactivity) in plasma.
- Volume of distribution at steady-state (V_{ss}) and clearance (CL) of parent after IV dose (Period 1 only)
- Renal clearance of parent (CL_r) after IV and oral administration
- Oral Clearance (CL/F) and apparent volume of distribution (V_z/F) for the parent following oral administration
- Direct evaluation of absolute bioavailability (F), indirect calculation of fraction of drug escaping first pass hepatic clearance (F_h), fraction absorbed (F_a) and fraction of drug escaping gut metabolism (F_g)
- Urinary and fecal cumulative excretion of total radioactivity as a percentage of the total radioactive dose (Period 1 and Period 2)

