5.2.1.1. Drug concentration measures

Refer to the Output and Programming Specification (OPS) document for Data Display Standards & Handling Conventions for Pharmacokinetic Data.

Plasma GSK3640254, [¹⁴C]- GSK3640254 and blood and Plasma total radioactivity concentration-time data will be listed for each participant and standard summary statistics will be calculated (i.e. arithmetic mean, standard deviation, median, minimum and maximum) by treatment and planned sampling time.

Individual participant, mean and median plasma GSK3640254, [¹⁴C]- GSK3640254 and total radioactivity concentration-time profiles will be plotted for each treatment on both a linear and semi-log scale.

For urine and feces, the total radioactivity excreted in urine and feces per sample or collection interval will be listed by subject. The cumulative total and the cumulative percentage of the total radioactive dose will be calculated and listed by subject. The concentration of radioactivity in urine, feces and fecal homogenates will be expressed as ng equivalents/g.

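### SAP Table 5 gives no valid formula for faecal recovery: the Ae[faeces] row repeats the urine formula, and total recovery is built on it

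*SAP*

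**What the plan says.** Excretion in urine and faeces as a percentage of the radioactive dose, in both periods, is a primary endpoint (Protocol Section 3; SAP Sections 1.2.1 and 5.2.1). SAP Section 5.2.2 says that Ae and Fe% will be summarised for urine, faeces and their total. The formulas are in SAP Table 5:

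- **Ae[faeces].** The description reads "Total radioactivity recovered in the urine (Ae[faeces]) calculated for each collection interval per subject and treatment period as". The formula under it is "Ae[urine]= (concentration in urine sample x collected sample weight) for each urine collection interval, eg 0-24, 24-48, etc", which is identical to the formula in the Ae[urine] row and has Ae[urine] on the left side.
- **Cumulative Ae[faeces].** The description reads "Cumulative total radioactivity recovered in the urine (Cumulative Ae[faeces]) calculated for each cumulative collection interval per subject and treatment period as". The formula sums Ae[faeces], but the collections to be summed are described as urine collections within the cumulative urine interval.
- **Fe%[faeces].** The description names the right parameter, "total radioactivity (Fe%[faeces]) for each collection interval per subject and treatment period". The formula divides Ae[faeces] by dose, but its left side is Fe%[urine].
- **Totals.** Ae[total] adds Ae[urine] and Ae[faeces]. Fe%[total] adds the two percentages.

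On what is measured, SAP Section 5.2.1.1 says "The concentration of radioactivity in urine, feces and fecal homogenates will be expressed as ng equivalents/g". SAP Table 2, which lists changes from the protocol analysis, mentions only the added Enrolled population.

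**The concern.** Table 5 is the working definition of a primary endpoint, and the row that should define the faecal amount contains no faecal quantity. Fe%[faeces], Ae[total], Fe%[total] and their cumulative forms all depend on that row. The only excretion data in the documents come from orally dosed rats and put almost everything in faeces, so the undefined term may well be the dominant one.

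Two details mean that the correction needs more than the word faeces in place of urine. The interval wording ties the cumulative sum to urine collections. And a concentration is planned in two faecal matrices, while the row names only one generic sample weight.

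**Working it through.** The documents state no expected recovery, so there is no figure of the plan's own to reproduce. The check compares the rows and then does simple mass-balance arithmetic.

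**Inputs**

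- Formulas: SAP Table 5, as set out above.
- Rat split: Protocol Appendix 6, data section, "0.04% urinary and 99.96% faecal excretion". These are oral rat data, expressed as shares of total excretion, not of dose.
- Home collection: Protocol Section 4.1.3. If excretion is still 1% or more in the last 24 h before Day 15 discharge, only faeces are collected at home.

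**Step 1: literal reading.** Let R be true total recovery (% of dose) and u the urinary share of what is excreted.

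- Correct: urine = uR, faeces = (1 − u)R, total = R.
- Table 5 taken literally: faeces = urine = uR, total = 2uR.

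| Urinary share u | R | Literal total (2uR) | Correct total |
|---|---|---|---|
| 0.04% (rat, oral) | 100% | 0.08% | 100% |
| 1% (assumed) | 100% | 2% | 100% |
| 30% (assumed) | 100% | 60% | 100% |
| 1% (assumed) | 90% | 1.8% | 90% |
| 30% (assumed) | 90% | 54% | 90% |

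The first line also assumes complete recovery. The human split is not in the documents, after either the oral or the IV dose, so the 1% to 30% range is only an assumption to show sensitivity.

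**Step 2: strict reading.** Because the pasted formula has Ae[urine] on its left side, the row can also be read as not defining Ae[faeces] at all. Then Fe%[faeces] and both totals have no defined faecal input.

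**Step 3: intervals.** Home collections after Day 15 have no urine counterpart. A cumulative sum restricted to urine intervals leaves them out, and they exist only for participants who excrete slowly.

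**Step 4: concentration and weight.** Two pairings give the amount in a faecal sample:

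- homogenate concentration × total homogenate weight;
- concentration per gram of faeces × faecal weight.

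Crossing them does not. If d is homogenate weight divided by stool weight, homogenate concentration × undiluted stool weight returns 1/d of the true amount. The documents give no d. For an assumed d of 2 to 5, that is 1/2 = 50% to 1/5 = 20% of true faecal recovery.

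**The case against.** The strongest reply is that this is a pasted row with unmistakable intent. Protocol Section 9.4.3 and SAP Section 5.2.1 state the endpoint correctly. Within Table 5 itself, Fe%[faeces] uses Ae[faeces] as numerator, the cumulative row sums Ae[faeces], and the totals add urine and faeces as separate terms. SAP Section 5.2 has the analytical CROs derive these parameters in their own reports, and the Study Reference Manual, which is not available here, may hold the right formula. Protocol Sections 4.1.2 and 4.1.3 base Period 2 discharge on scintillation counting of urine and faecal homogenates, independently of Table 5. A total near 0.08% would clash with those results at once.

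All of this stands. A reader might infer from Table 5 that the primary endpoint itself is wrong, or that someone would compute faecal recovery from urine; the documents do not support either. The reply does not supply the missing formula, though, and the discharge check covers Period 2 only.

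A reader might also infer that, once the word is changed, recovery will be understated by the homogenate dilution. That is not established. SAP Section 5.2.1.1 plans concentrations in both faeces and faecal homogenates, and faecal concentration × faecal weight would be valid. No section prescribes the wrong pairing; the SAP simply does not say which pairing applies.

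**Conclusion.** The point holds as a defect in an operative definition. Table 5 has no valid formula for Ae[faeces], and three rows carry urine wording. Followed literally, total recovery becomes twice urinary recovery: 0.08% instead of 100% of dose under the oral rat split and complete recovery, and 2% to 60% over an assumed urinary share of 1% to 30%. Errors near the bottom of that range would be noticed. The less visible risks are the omission of faecal-only home collections and a mismatched concentration and weight. The first depends on whether any participant needs home collection; the second is conditional on a pairing that the SAP leaves open, and its size rests on a dilution ratio that the documents do not give.

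The change should be made because the endpoint is primary and the correction is simple. Nothing here shows that the discharge decisions are affected.

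**What to change.** Amend SAP Table 5:

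1. Ae[faeces] = faecal radioactivity concentration × the matching weight, summed over the samples in each faecal collection interval. State the pairing explicitly: homogenate concentration with total homogenate weight, or concentration per gram of faeces with faecal weight.
2. Fe%[faeces] = Ae[faeces] / radiometric dose × 100, with the left-hand label corrected. The arithmetic on the right is already sound.
3. Cumulative Ae[faeces] and Cumulative Fe%[faeces] = sums over faecal collection intervals, including home collections after Day 15. Remove the urine wording.

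While the section is open, reconcile who derives these parameters: SAP Section 5.2 names the analytical CROs, and Section 5.2.1.2.2 names the sponsor's DMPK department.

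The cost is SAP wording only; no new samples, visits or data are needed.

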8.5.4. Vomitus collection (if occurs)

Any episodes of vomiting should be recorded in the CRF as an adverse event.

If a participant vomits within the first 4 h after oral dosing, the participant will be considered unsuitable for evaluation and will be withdrawn from the study. Even if withdrawn, participants should remain in the clinic and samples collected until the discharge criteria outlined in Section [4.1.3](#) are met. Should the participant vomit after the first 4 h post oral dosing, the participant will not be withdrawn.

If a participant vomits any time during or after IV dosing, the participant will not be withdrawn.

As practical, the vomitus will be collected and the amount of radioactivity present in the vomitus estimated, using the sample handling procedure described for quantifying radioactivity in stools. During dosing, staff should ensure that each participant has a suitable pre-weighed plastic collection vessel available for that purpose.

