9.4.3. Pharmacokinetic Analyses

Plasma GSK3640254 concentration-time data will be listed for each participant and summarised by treatment and planned sampling time. [¹⁴C]-GSK3640254 and radioactivity concentrations in whole blood and plasma will be reported similarly. Individual participant, mean and median plasma GSK3640254, [¹⁴C]-GSK3640254, and total radioactivity concentration-time profiles will be plotted for each treatment on both a linear and semi-log scale.

Pharmacokinetic analysis will be performed by or under the direct auspices of Clinical Pharmacology Modelling & Simulation, GSK. Plasma GSK3640254, [¹⁴C]-GSK3640254, and total radioactivity concentration-time data will be analysed by non-compartmental methods with WinNonlin Version 6.3 or above. Calculations will be based on the actual sampling times recorded during the study. From the plasma concentration-time data the following pharmacokinetic parameters will be determined, for GSK3640254, [¹⁴C]-GSK3640254, and total radioactivity (whole blood and plasma) as data permits: maximum observed plasma concentration (C_{max}), time to C_{max} (t_{max}), AUC(0-t) and AUC(0-inf), terminal phase rate constant (λ_z), and apparent terminal phase half-life ($t_{1/2}$) following oral and IV dosing. Additionally, V_{ss} , CL_r , and CL will be derived following IV dosing and CL/F and V_z/F will be derived following oral dosing. These parameters will be summarised descriptively.

Absolute bioavailability will be estimated for oral dose for each participant and will be summarized.

Derivation of the urine and fecal radioactivity parameters will be through support provided by CRO partners. The following radioactivity parameters will be determined from the urine and fecal radiolabelled drug-related material (total radioactivity) data, and will be listed and summarised by treatment:

- Percentage excreted in urine (Fe%[urine]) within each collection period and cumulative urinary recovery and fraction excreted over the total collection period.
- Percentage excreted in feces (Fe%[fecal]) with each collection period and cumulative fecal recovery and fraction excreted over the total collection period and cumulatively over the collection period.

- Total excretion (sum of urine and fecal excretion), Fe% [total] will be calculated by collection interval for each participant.

The urine, fecal and total radioactivity parameters will be listed, summarised and plotted, as appropriate.

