1.2. Objectives, Endpoints and Estimands

1.2.1. Objectives and Endpoints

Objectives	Endpoints ¹
Primary	

 To determine parent GSK3640254 and total drug-related radioactivity systemic concentrations following a single IV microtracer dose of [¹⁴C]-GSK3640254 (with an oral dose of non-radiolabelled 	
 AUC(0–inf), AUC(0–t), Cmax, tmax and t1/2 of parent and total drug-related material (radioactivity) in plasma and blood.

CONFIDENTIAL

Statistical Analysis Plan 213051

Objectives	Endpoints ¹
GSK3640254) and oral dose of [¹⁴ C]-GSK3640254 ¹	
 Volume of distribution at steady state (V_{ss}) and clearance (CL) of parent after IV dose (Period 1 only). Renal clearance of parent (CL_r) after both IV and oral dose Oral clearance (CL/F) and apparent volume of distribution (V_z/F) for the parent following oral administration

 To calculate the absolute oral bioavailability of GSK3640254 	
 Direct estimation of absolute oral bioavailability (F), indirect calculation of fraction of drug escaping first pass hepatic clearance (F_h), fraction absorbed (F_a) and fraction of drug escaping gut metabolism (F_g).

 To determine the rate and extent of excretion of total radioactivity in urine and feces and the total recovery of radioactivity, following IV and oral administrations of [¹⁴C]-GSK3640254 	
 Urinary and fecal cumulative excretion as a percentage of the total radioactive dose
Secondary	

 To evaluate the safety and tolerability of GSK3640254 after single IV and oral doses in healthy participants. 	
 Characterize observed adverse events, and abnormal laboratory, 12-lead ECG, and vital signs assessments observed.

 To determine the blood:plasma ratio of [¹⁴C]-GSK3640254-related materials (total radioactivity) associated with blood cellular components 	
 Blood:plasma ratio of [¹⁴C]-GSK3640254-related materials (total radioactivity).
Exploratory	

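### Total recovery of radioactivity counts urine and faeces only, so it is understated by whatever share of the labelled dose is vomited, essentially a Period 2 issue

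*SAP*

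**What the plan says.** The third primary objective covers the rate and extent of urinary and faecal excretion and also "the total recovery of radioactivity, following IV and oral administrations of" the labelled drug (SAP 1.2.1; Protocol 3 has the same objective). Its endpoint is cumulative urinary and faecal excretion as a percentage of the radioactive dose.

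SAP 5.2.1.2.2, Table 5, describes the total as "Total radioactivity recovered in total excretum (sum of urine and faecal excretion") and gives the formula "Ae[total] = Ae[urine] + Ae[faeces"]. Fe%[total] and the cumulative versions follow the same pattern. The denominator of Fe% is the radiometric IV dose in Period 1 and the radiometric oral dose in Period 2, with no deduction for vomited dose. SAP 5.2.2 again describes the total as urine plus faeces, and Protocol 9.4.3 agrees: "Total excretion (sum of urine and fecal excretion), Fe% [total] will be calculated by collection interval for each participant".

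Protocol 8.5.4 deals with a third matrix: "As practical, the vomitus will be collected and the amount of radioactivity present in the vomitus estimated". It also sets a time rule. For early vomiting: "If a participant vomits within the first 4 h after oral dosing, the participant will be considered unsuitable for evaluation and will be withdrawn"; excreta are still collected from that participant until the discharge criteria are met. For later vomiting: "Should the participant vomit after the first 4 h post oral dosing, the participant will not be withdrawn". Vomiting during or after the IV dose does not lead to withdrawal either. Protocol 7.2 is softer on early vomiting and says only that withdrawal may be considered.

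The PK analysis set (Protocol 9.3, SAP 4) requires one non-missing PK assessment and has no exclusion for vomiting. SAP Table 3 applies a treatment-policy strategy to withdrawal and adverse events, with no adjustment.

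**The concern.** A mass-balance total should account for label found in every matrix assayed. Here vomited label stays in the denominator, because the dose is the full radiometric dose, but can never enter the numerator. A collection that accounts for nearly all the radioactivity would then read as incomplete. With four to six participants, one such case is enough to move the group mean.

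The event is plausible under the study's own procedures, although the documents give no vomiting rate. In Period 2 the bile string is swallowed 2 h after the labelled dose, a high-fat food cue follows at 5.5 h and the string is withdrawn at 7 h (Protocol 4.1.2). Protocol 2.3.1 lists gagging on retrieval and gastrointestinal intolerability as risks. Retrieval falls after the 4 h cut-off, so a participant who vomited at that point would stay in the study and in the recovery summary.

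**Working it through.** The plan states no figure to reproduce, so the check is mass-balance arithmetic.

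**Inputs**
- n = 6 enrolled, at least 4 completing (SAP 1.3).
- Denominator: full radiometric dose (SAP Table 5).
- Recovery threshold for discharge in Period 2: above 90% (Protocol 4.1.3).
- v = percent of the radioactive dose in vomitus. The documents do not give it; 0–30% is assumed.
- R = true recovery over all matrices, in percent of dose. It is also not given; 92, 95 and 100% are used as illustrations.

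**Formulas**
- Reported Fe%[total] for the participant = R − v.
- Shift in the group mean with one such participant = v/n.

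**Results with R = 95%**

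| v (% of dose) | Reported urine + faeces | With vomitus | Mean falls by, n = 6 | Mean falls by, n = 4 |
|---|---|---|---|---|
| 0 | 95 | 95 | 0 | 0 |
| 1 | 94 | 95 | 0.17 | 0.25 |
| 5 | 90 | 95 | 0.83 | 1.25 |
| 10 | 85 | 95 | 1.67 | 2.50 |
| 20 | 75 | 95 | 3.33 | 5.00 |
| 30 | 65 | 95 | 5.00 | 7.50 |

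Example: one participant vomits 20% of the dose and everyone has R = 95%. The reported mean is (5 × 95 + 75)/6 = 91.7% with six participants, or (3 × 95 + 75)/4 = 90.0% with four, against 95% with vomitus counted.

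**The 90% threshold.** Urine plus faeces exceeds 90% only if v < R − 90. It therefore fails from v = 10% at R = 100%, from v = 5% at R = 95% and from v = 2% at R = 92%.

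**When v can be above zero.** In Period 1 the tablet is unlabelled and the infusion begins 5 h after it, so vomitus before 5 h holds no Period 1 label (v = 0). After the infusion starts, only label secreted into the gut could be vomited. In Period 2 the oral dose itself carries the label. That is the period in which v could be material.

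**Who stays in the summary.** After 4 h: not withdrawn, so included. Within 4 h: described as unsuitable for evaluation, yet still sampled and not removed by the PK set definition. That second group could show the largest v, because more of the labelled dose may be unabsorbed.

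**The case against.** The strongest reply is that the formula does what the endpoint says. The endpoint is urinary and faecal excretion, Protocol 9.4.3 fixes the sum, and the SAP implements and labels it openly. Regurgitated dose may never have been absorbed, so counting it as excretion would be wrong. This part stands, and it is a reason to leave the excretion parameters alone. It does not justify letting the same sum serve as total recovery, which the objective names separately.

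It can also be said that Table 5 allows additional parameters as required, that display and handling detail is left to a separate Output and Programming Specification, and that every vomiting episode is recorded as an adverse event, so a low value could be explained. These are general openings. None names vomitus, and they leave its inclusion to be settled after results are known.

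The vomitus figure is only an estimate, obtained as practical. That is a fair reason to show totals with and without it.

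Three stronger readings are tempting and not supported:
- A reader might infer that recovery is understated at every vomiting episode. It is not: vomitus before the Period 1 infusion carries no Period 1 label.
- A reader might infer that most participants who vomit are kept. The documents give a time rule and no rates, and the gastrointestinal events listed in Protocol 2.3.1 for the earlier multiple-dose study do not include vomiting.
- A reader might infer that a participant who vomits 10% of the dose cannot be discharged. Discharge follows Protocol 4.1.3, not SAP Table 5. It has a second route (below 1% of dose in two consecutive 24 h periods) and a Day 15 limit. Protocol 4.1.3 does not say whether vomitus counts toward its recovery figure.

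**Conclusion.** The point holds as a narrow, conditional one. As written, the total recovery parameter omits a matrix whose radioactivity the protocol plans to estimate, and it keeps the full dose as denominator. When labelled material is vomited, reported recovery is too low by exactly v for that participant and by v/n for the mean. With one such participant and an assumed v of 1–30%, the mean falls by 0.17–5.0 points (n = 6) or 0.25–7.5 points (n = 4). If the vomitus holds no label, nothing changes. The range for v is an assumption, and both the probability of vomiting and its size are unknown from the documents. The consequence lies in the reported primary result, essentially in Period 2. This is a minor point, worth settling beforehand because it bears on a primary objective and is cheap to correct.

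**What to change.** In the SAP:
- Keep Fe%[urine], Fe%[faeces] and their sum, and label that sum as excretion.
- Add Ae[vomitus] and Fe%[vomitus] to Table 5.
- Define total recovery = urine + faeces + vomitus (if any), with a cumulative version, and report it alongside the urine-plus-faeces total.
- List vomitus radioactivity separately by participant, with time after dose and a note that the estimate may be incomplete.
- State whether participants described as unsuitable for evaluation after early vomiting enter the recovery summaries.
- Record the addition in SAP Table 2 as a change from Protocol 9.4.3.

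In the protocol, state whether vomitus counts in the recovery figure of Section 4.1.3. Sections 7.2 and 8.5.4 differ on withdrawal after early vomiting and must be reconciled.

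The cost is a short text change and one extra row in the recovery displays, using data already planned. The small downside is that an approximate quantity enters one of the totals, which is why both should be shown.
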